## 1. Objectives / Specific Aims

The objectives of the study are to:

- determine if once weekly dosed isotretinoin is effective for moderate acne vulgaris
- evaluate patient satisfaction with once weekly dosed isotretinoin for moderate acne vulgaris treatment
- identify any adverse effects associated with once weekly dosed isotretinoin for moderate acne vulgaris treatment

Once weekly isotretinoin dosing has the potential to significantly improve moderate acne with good patient satisfaction and safety profile; however, no study findings on this treatment option have been published to date. The efficacy of isotretinoin, an oral vitamin A derivative, for treatment of acne has been well established. The traditional treatment course for severe acne consists of once to twice daily dosing (0.5-1 mg/kg/day) for 4-7 months (or 150mg/kg total cumulative dose). Though efficacious, there are numerous reported side-effects due to achieving the cumulative dose rapidly by once to twice daily dosing, such as severe dry skin, lips, and eyes, as well as liver enzyme and lipid abnormalities. Because of this, there have been studies exploring alternative isotretinoin dosing regimens including microdose, lower daily dose regimens (0.15-0.4 mg/kg/day, 0.25-0.4 mg/kg/day, 0.3-0.4 mg/kg/day, in addition to 5 mg/day and 0.15-0.28 mg/kg/day with additional of local application of 1% clindamycin gel every other day) and daily dosing for 7-10 consecutive days (0.5-0.7 mg/kg/day) out of each month only. All studies had favorable outcomes with alternative dosing, despite the lower total cumulative dose versus conventional dosing. Those who also analyzed adverse effect rates with alternative isotretinoin dosing found that these were either rarely observed or similar to conventional dosing. In contrast, the potential adverse effects of oral antibiotics used for acne include photosensitivity and nausea/vomiting (doxycycline), drug-induced pigment deposition and drug-induced systemic lupus erythematosus

(minocycline), and angioedema and drug rashes including drug reaction with eosinophilia and systemic symptoms (DRESS) syndrome (trimethoprim-sulfamethoxazole). Interestingly, rates of acne recurrence between alternative isotretinoin dosing and conventional dosing were similar at follow-up, despite a much older study from 1984 that found otherwise. Additionally, cost of alternative isotretinoin dosing was lower than with conventional dosing, and patient satisfaction was highest in the alternative dosing groups.

### 3.0 Intervention to be studied (if applicable)

Intervention: once weekly dosing of isotretinoin (1-1.5 mg/kg/week)

- FDA status: approved for moderate-severe acne vulgaris in ages 12 and older
- Please see Background for rationale on proposed dosing method
- Pharmacology: an oral retinoid (vitamin A derivative) that is thought to improve acne by decreasing sebaceous gland proliferation and function, though the exact mechanism is unknown. It is a lipophilic medication that is bound to plasma proteins; eating a high fat meal with the medication increases its bioavailability but not its half life (21 hours). It is metabolized into 4-oxo-retinoic acid, 4-oxo-isotretinoin, and tretinoin. It is excreted through the feces and urine. Improvement of acne is due to drug accumulation. Drug serum concentration returns to physiologic level after about 2 weeks of taking the drug.
- Safety: isotretinoin use is most commonly associated with xerosis and cheilitis. It can more rarely be associated with hypersensitivity reactions, hypertriglyceridemia, hepatitis, agranulocytosis, musculoskeletal symptoms, pseudotumor cerebri, mood swings including depression, delayed wound healing, hearing impairment, and decreased night vision and corneal opacities. It can cause birth defects in women who become pregnant while taking the medication. There is a potential association with worsening of inflammatory bowel disease. Because of this, all patients (men and women) who take isotretinoin must enroll in the IPLEDGE program prior to administration of medication.

16) FDA drug information, isotretinoin, Roche Laboratories.

([https://www.accessdata.fda.gov/drugsatfda\\_docs/label/2008/018662s059lbl.pdf](https://www.accessdata.fda.gov/drugsatfda_docs/label/2008/018662s059lbl.pdf))

### 4.0 Study Endpoints (if applicable)

Primary endpoint: efficacy

Secondary endpoints: patient satisfaction, adverse effects

### 5.0 Inclusion and Exclusion Criteria/ Study Population

#### Inclusion Criteria

- English-speaking patients 12 years and older with the diagnosis of moderate acne vulgaris

#### Exclusion Criteria

- Patients who are at baseline on long-term tetracycline antibiotics, long-term trimethoprim-sulfamethoxazole, or on spironolactone for any reason
- Patients who have taken isotretinoin in the past 6 months

- Patients with hypersensitivity to isotretinoin or to any of its components
- Females who are pregnant, likely to become pregnant, or will be breast-feeding during the study period
- Patients with a history of major depression, mania, or psychosis with an active episode during the past year including current psychotic symptoms and/or current suicidal ideation
- Adult patients with cognitive impairment
- Patients with baseline kidney or liver disease
- Patients with baseline hypertriglyceridemia
- Patients with history of or current pseudotumor cerebri
- Patients with any clinically significant unstable medical condition which could pose a risk to the safety of the patient
- Inability or unwillingness of subject or legal guardian/representative to give informed consent

## **6.0 Number of Subjects**

Target enrollment is 50 participants to allow for attrition. Minimum expected enrollment is 30 participants.

## **7.0 Setting**

Study site: outpatient dermatology clinics at MUSC.

## **8.0 Recruitment Methods**

- Recruitment will occur during standard of care visits to the Dermatology Clinics including its virtual visits.
- The first person to inform eligible patients about the study will be a clinician directly involved in the eligible patient's care. The clinician will first determine if the patient may meet criteria (score of 3, moderate acne, on CASS clinical scale as described in more detail in section 10.0). If the patient expresses interest in the study, the clinician or study co-investigators will approach the patient without coercion and with the emphasis on the voluntary aspect of being enrolled in this study. He/she will also be told in a caring manner that no matter his/her decision, it will not affect his/her care. This discussion will take place either in-person during the patient's clinic appointment or over telephone within one business day of the appointment.
- If the discussion takes place in-person during the clinic appointment, the patient will be provided a printed recruitment pamphlet reiterating the information regarding the study (**attachment A**). Eligible patients who agree to participate will sign the study consent form. Weight will be obtained. A baseline photograph will be taken and uploaded into the patient's medical chart (Epic). Two baseline surveys (Dermatology Life Quality Index survey to assess patient satisfaction and a second survey regarding potential isotretinoin adverse effects) will be completed by the patient (**attachments B and C, respectively**). The patient's clinician will then counsel the patient on isotretinoin and IPLEDGE and enroll the patient in the IPLEDGE system following all prompts. The clinician will order baseline laboratory blood work (all patients) and

urinary pregnancy test (females). Once blood work has returned and is without any clinically significant abnormalities (see section 13.0), the weekly isotretinoin (at dose 1-1.5 mg/kg per week) will be prescribed by the clinician (for males). Females will need to wait an additional month to have a second negative pregnancy test before starting the medication per IPLEDGE standard of care. After a second negative pregnancy test at next monthly visit, the clinician can prescribe the weekly dosed isotretinoin.

- For any patient who is seeing his or her provider through a virtual visit and is interested in participating in the study, a study investigator can either counsel the potential participant in the provider's clinic (via virtual platform) or can call the patient to counsel over the phone. Consent can be obtained electronically (per REDCap guidelines). These patients will then have an in-person clinic visit scheduled with their provider to enroll in IPLEDGE so that the medication can be prescribed. Weight will be obtained. A baseline photograph will be taken and uploaded into the patient's medical chart (Epic). Two baseline surveys (Dermatology Life Quality Index survey to assess patient satisfaction and a second survey regarding potential isotretinoin adverse effects) will be completed by the patient (**attachments B and C, respectively**). The patient's clinician will then counsel the patient on isotretinoin and IPLEDGE and enroll the patient in the IPLEDGE system following all prompts. The clinician will order baseline laboratory blood work (all patients) and urinary pregnancy test (females). Once blood work has returned and is without any clinically significant abnormalities (see section 13.0), the weekly isotretinoin (at dose 1-1.5 mg/kg per week) will be prescribed by the clinician (for males). Females will need to wait an additional month to have a second negative pregnancy test before starting the medication per IPLEDGE standard of care. After a second negative pregnancy test at next monthly visit, the clinician can prescribe the weekly dosed isotretinoin.
- Additionally, if a study investigator is not available to counsel the patient at the time of the patient's clinic visit, and the clinician believes that the patient may qualify for the study, the clinician will send an Epic electronic health record message to the Study Coordinator (Dermatology research fellow) with the attached patient chart. The Study Coordinator will contact the patient by telephone within one business day. Over the phone, the study investigator will assess if the patient is eligible for the study and if he/she would like to participate. If so, an additional clinic visit (either in-person or virtual) will be set up with the patient's clinician to obtain a baseline photograph (alternatively the patient can also upload their own photos into MyChart), as well as to enroll the patient into IPLEDGE after counseling on the system and isotretinoin medication. Two baseline surveys (**attachments B and C**) and the study consent form (**attachment E**) will be sent electronically (per REDCap guidelines) for signature. These steps are outlined in directions for providers, a pamphlet that will be printed in each clinic site (**attachment D**). The signed consent form and two completed surveys can either be emailed back to the Study Coordinator for upload into the patient's medical chart (Epic) or photos of these can be taken by the patient for upload into their medical chart via MyChart (Epic). Once the patient is enrolled in both the study and IPLEDGE and is medically cleared to start isotretinoin, the clinician will prescribe the medication at the weekly study dose.

- No study-only procedures will be performed without first obtaining informed consent. Any standard of care procedures, tests, or visits can be completed at any time per clinical care team.
- The study will be posted on the new MUSC Dermatology Research Website. The study name, inclusion criteria and brief description of the study design will be posted. Patients interested in participating in the study will make an appointment with a member of the MUSC Dermatology Team as they must be followed by a dermatologist to receive their medication and have labs completed per standard of care IPLEDGE protocol.

## 9.0 Consent Process

- Study consent form is attached (**attachment E**). The method of obtaining consent including where this will take place and how this will be completed is detailed in above section 8.0. Counseling about the study and about the isotretinoin medication will take place prior to any signing of the study consent form. The participant will be asked to repeat back to the provider his or her understanding of the study and potential risks/benefits of the medication. The consent form for the study will be signed by the participant if the patient agrees to enroll in the study after counseling by a Study Coordinator. The participant will also enroll in IPLEDGE (isotretinoin monitoring system) with the help of the clinician where he or she will sign IPLEDGE consent forms.
- For participants who are not yet adults, parental permission will be obtained to enroll the participant with the participant's blessing. Assent will be obtained from all children during enrollment. If the participant turns eighteen during the study period, the participant will then provide written consent to continue the study; this will occur either in-person at a clinical visit or through electronic consent with a study investigator. Cognitively impaired adults are excluded from the study population.
- All participants will be reminded at each monthly follow-up visit that they can remove themselves from the study at any time.

## 10.0 Study Design / Methods

This will be an open-label, prospective, proof-of-concept study of patients with moderate inflammatory acne. The patients will be treated for at least 4 months.

- The initial acne assessment will be performed by dermatologists and dermatology residents using a validated, clinical grading system (Comprehensive Acne Severity Scale, CASS as below) with lesion counts (inflammatory and noninflammatory). Only moderate acne patients who are eligible for enrollment will be allowed to participate. Recruitment methods are outlined in above section 8.0. A baseline photo will be taken and placed in the patient's medical chart (Epic).

# ASSESSMENT

## ASSESSING SEVERITY OF ACNE

A new grading system named Comprehensive Acne Severity Scale – CASS (modification of an Investigator Global Assessment [IGA] of Acne Severity) is a validated tool which significantly correlates with the Leeds technique for face, chest and back. It is simpler to use in clinical practice.

**Table 3: Comprehensive Acne Severity Scale (CASS)**

GRADE*		DESCRIPTION
Clear	0	No lesions to barely noticeable ones. Very few scattered comedones and papules.
Almost clear	1	Hardly visible from 2.5 metre away. A few scattered comedones, few small papules and very few pustules.
Mild	2	Easily recognisable; less than half of the affected area is involved. Many comedones, papules and pustules.
Moderate	3	More than half of the affected area is involved. Numerous comedones, papules and pustules.
Severe	4	Entire area is involved. Covered with comedones, numerous pustules and papules, a few nodules and cyst.
Very severe	5	Highly inflammatory acne covering the affected area, with nodules and cyst present.

Inspection is done at a distance of 2.5 meters away for acne on face, chest and back.

▪ **Chest area defined as:**

Anterior torso superiorly defined by suprasternal notch extending laterally to shoulders and inferiorly by a horizontal line defined by the xiphoid process.

▪ **Back area defined as:**

(Is demarcated by the) superior aspects of the shoulders extending to the neck and inferiorly by the costal margins.

- The participants will be treated with once weekly isotretinoin at a dosage of 1-1.5mg/kg/week. Exact dosage will be determined by the provider.
- Efficacy will be determined by having one trained individual (“Photo Reviewer”) grade patients’ facial photographs to limit interrater reliability bias. This person will not be told what is being used as the study drug, and will not be told any details of the study, including that all participants are on the study drug, in order to limit observer bias (blinded). Every month, clinical photos will be submitted for each patient enrolled in the study. The participants will have these photos taken at monthly follow-up visits (monthly follow-up visits are standard of care per requirements of IPLEDGE, the medication monitoring system for isotretinoin). For in-person visits, these monthly photos will be taken by the provider or staff in clinic and directly uploaded to the Epic electronic medical record. For any virtual clinic visits (given the COVID-19 pandemic), the monthly photos will be submitted into MyChart by the patient.
- The Study Coordinator (Dermatology research fellow), who per the study consent form has permission to access participants’ medical records for the purpose of the study, will follow each patient through Epic electronic medical record to confirm that photos are submitted in a timely manner.
- A separately trained individual (“Data Retriever”), who per the study consent form has permission to access participants’ medical records for the purpose of the study, will submit any uploaded photos (baseline and at the end of each

month) from Epic to the Photo Reviewer by secure, encrypted email, labeling only with participant number and date of photo. This ensures that the Photo Reviewer is always reviewing only individual photos and will not ever enter the patient's medical chart to further limit bias.

- Photo Reviewer will receive photos and document a monthly CASS grade for each participant (in encrypted Excel only accessible by study team members, using study participant numbers without patient identifiers, **attachment F**). Baseline photos will all be a grade 3 (moderate) based on study inclusion criteria. "Improvement" is defined as decrease in grade from a 3 (moderate) to either a 2 (mild), 1 (almost clear), or 0 (clear). "Failure" is defined as showing no improvement (remaining a grade 3), increasing grade of 4 (severe) or 5 (very severe), or requiring additional oral treatment (for example, worsening acne requiring conventional dose isotretinoin). Treatment success can then be calculated as the percentage of participants with improvement out of the total number of participants at the end of four months, in addition to treatment success after each month of treatment.
- Any participants who take any oral tetracycline antibiotics or trimethoprim-sulfamethoxazole during the study period (for a reason besides acne) will be removed from the study in order to prevent any confounding. Patients requiring these medications for acne after the study period has begun will remain included in the study and will be listed as intervention "failure" as above. Participants will be allowed to continue use of topical acne cleansers and treatments during the study as per standard of care.
- Photo Reviewer will be a blinded medical student because all of the dermatology residents will be participating in the clinical care of study participants. The Photo Reviewer will be trained by the Primary Investigator (Dermatology Resident) and Study Coordinator (Dermatology Research Fellow) on how to use the objective CASS grading system.
- Data Retriever will be a Dermatology resident who will be trained by the Primary Investigator (Dermatology Resident) and Study Coordinator (Dermatology Research Fellow).
- All participants, regardless of whether they show "improvement" or "failure," will be followed for up to four months after the study period to assess for recurrence of acne. During this period, any further treatment decisions will be made by the patient and his or her clinician. Any participants who choose to continue once weekly isotretinoin will be asked to upload clinical photos and patient satisfaction surveys monthly through MyChart. Other participants who discontinue the isotretinoin will be asked about their follow-up acne treatment.

To determine patient adverse effects (secondary endpoint), we will monitor for side-effects of the interventional medication.

- Per standard of care, patients will be enrolled in IPLEDGE, requiring extensive counseling before starting the isotretinoin medication, monthly follow-up visits for males and females, and monthly urine pregnancy tests for females.
- Each patient will fill out a survey at baseline (**attachment C**) and at each monthly visit (**attachment G**) inquiring about potential side-effects of isotretinoin (with severity) including dry skin, dry mucous membranes (lips,

eyes), GI upset, bone or muscle pain, night vision abnormalities, mood swings/depression, headaches, delayed wound healing. If the follow-up visit between the patient and his or her clinician is virtual, the attached surveys will be sent in an encrypted email for completion by the participant. Photos of each completed survey will be uploaded into the patient's chart either at their clinic visit or by the patient via MyChart (virtual visit).

- Per standard of care, laboratory blood work (CBC, CMP, lipid panel) will be obtained prior to starting the medication and will be repeated two months into the study period (after two clinical follow-up visits, also per standard of care and confirmed by PRA), or more frequently if clinically indicated. The results will be reviewed from the medical record.
- Pregnancy test data will be collected from the medical record as these will be performed as part of the clinical care of the patient. Female participant's individual providers will order pregnancy tests, which per standard of care are typically collected at baseline x 2 (one month apart), every month while on the medication, and at least one month after stopping the medication. If patients have any significant laboratory abnormalities that could be related to the medication, the medication will be discontinued.
- The Study Coordinator (Dermatology research fellow) will follow each patient through Epic electronic medical record to confirm that laboratory work and surveys are completed in a timely manner.
- Data Retriever will follow each participant's laboratory blood work and any abnormalities will be entered into the encrypted Excel sheet; this individual will also enter all survey responses into the same encrypted Excel sheet (attachment F).

To determine patient satisfaction (secondary endpoint), the Dermatology Life Quality Index (<https://www.cardiff.ac.uk/medicine/resources/quality-of-life-questionnaires/dermatology-life-quality-index>) will be administered at baseline before receiving any medication and at each monthly follow-up visit. The DLQI is the most frequently used validated, patient-reported outcome measure in dermatology trials (attachment B). License for use of survey has been obtained (attachment H).

- Data Retriever will follow each participant's surveys and enter information into the same encrypted Excel sheet as noted above.

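### Entry requires CASS grade 3 at no stated body site, but efficacy is graded on the face only, so a facial baseline of 3 is not secured and truncal acne reaches the endpoint only through added oral treatment

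*Protocol*

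**What the plan says.** **Objective (section 1).** The study is to "determine if once weekly dosed isotretinoin is effective for moderate acne vulgaris". No body site is named.

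**Entry (sections 5.0, 8.0 and 10.0).** The inclusion criterion is "English-speaking patients 12 years and older with the diagnosis of moderate acne vulgaris". Section 8.0 gives the working threshold as "score of 3, moderate acne, on CASS clinical scale as described in more detail in section 10.0". Section 10.0 has dermatologists and residents make the initial assessment by CASS and lesion counts. None of these statements says where on the body the grade of 3 must be found.

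**Scale (section 10.0, Table 3 and its notes).** "Inspection is done at a distance of 2.5 meters away for acne on face, chest and back". Anatomical borders for the chest and back follow.

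**Efficacy reading (section 10.0).** A single blinded Photo Reviewer grades "facial photographs to limit interrater reliability bias". The monthly collection sentence is looser: "Every month, clinical photos will be submitted for each patient enrolled in the study". It names no site.

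**Endpoint definition (section 10.0).** "Baseline photos will all be a grade 3 (moderate) based on study inclusion criteria". Improvement is a fall from that 3 to 2, 1 or 0. Failure is staying at 3, rising to 4 or 5, or needing further oral therapy for acne. Success is the share of participants improved at four months, also reported month by month.

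**The concern.** Three parts of the design use different areas of skin. Entry and the objective are open to acne at any CASS site, whereas the graded outcome is confined to the face. Two things follow.

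First, the endpoint is a change from an assumed starting value of 3. If the qualifying grade can come from the chest or back, the facial starting value need not be 3, and the definition of improvement has no firm starting point for that participant.

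Second, a participant with both facial and truncal acne is judged on the face alone unless further oral treatment is needed. The study is a single-arm, open-label proof of concept, and section 12.0 says that observations will be reported without statistical analysis. The raw success percentage is therefore the result, and no comparison group shares the same measurement rule. A statement about moderate acne vulgaris in general would rest on facial response.

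**Working it through.** The protocol has no figure to reproduce here: the enrolment numbers come without a derivation, and no success rate is hypothesised. The check is a comparison of the rules, followed by simple arithmetic.

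**Step 1. Is a facial baseline of 3 guaranteed?** Section 10.0 derives it from the inclusion criteria. Those criteria require moderate acne (section 5.0) and CASS 3 (section 8.0), and section 8.0 points to the three-site scale in section 10.0. CASS 3 on the back with CASS 2 on the face satisfies that wording. The statement about baseline photographs is therefore an assumption and not a consequence of the criteria.

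**Step 2. Apply the endpoint rules to typical cases.**

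| Entry grades | Course at four months | Further oral acne treatment? | Result under section 10.0 |
|---|---|---|---|
| Face 3, trunk clear | Face 2 | No | Improved, as intended |
| Face 3, trunk 3 | Face 2, trunk 3 or 4 | No | Improved; trunk not counted |
| Face 3, trunk 3 | Face 2, trunk 4 | Yes | Failure, whatever the face shows |
| Face 2, trunk 3 | Face 2, trunk 3 | No | Improved if the baseline is taken as 3; undefined if the actual facial baseline is used |
| Face 2, trunk 3 | Face 2, trunk 1 | No | Same two readings, although the trunk responded |

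In the last two rows the facial grade is 2 throughout. If every baseline is presumed to be 3, that reads as a success with no facial change. If the true facial baseline is used, there is no fall from 3, but the participant has not stayed at 3 or risen above it either. The case then fits neither definition.

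**Step 3. Size per participant.** Inputs: target enrolment 50 and minimum expected enrolment 30 (section 6.0). One participant wrongly counted as improved changes the success percentage by 100 × 1/N.

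- N = 50: 100 × 1/50 = 2.0 percentage points.
- N = 30: 100 × 1/30 = 3.3 percentage points.

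The number affected, k, is not given in the document. As an assumption only, k = 1 to 5 gives 100 × k/N:

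- N = 50: 2.0 to 10.0 points.
- N = 30: 3.3 to 16.7 points.

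These figures treat all enrolled participants as the denominator. With fewer participants at month four, each one counts for more.

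**The case against.** The case for leaving the text alone has substance.

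- **Oral treatment counts as failure at any site.** Section 10.0 makes no reference to body site when it classes further oral treatment for acne, including antibiotics, as failure, and clinicians see participants monthly. A reader might infer that truncal acne can never be detected and that such a participant always counts as improved. The document does not support that. What stands is narrower: truncal acne that persists, or worsens without leading to oral treatment, is not counted.
- **Truncal images are not excluded.** The monthly collection sentence refers to clinical photographs in general. That is correct, but nothing requires chest or back images, and the efficacy sentence specifies facial ones.
- **The baseline sentence shows that facial grade 3 was intended.** This is plausible. If so, the entry criteria should say it, because the clinician who screens the patient works from those criteria.
- **The chest and back text is reproduced scale material.** No study procedure says that those areas will be graded. This limits its weight, but section 8.0 refers to that scale for entry without restricting it.
- **Facial grading by one blinded reader is a reasonable choice in a small proof-of-concept study.** Agreed. The problem is that entry and claim do not match the choice.

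**Conclusion.** The mismatch is real, and the wording of the protocol is enough to show it. Entry does not secure the facial baseline of 3 on which the definition of improvement depends. Truncal acne affects the endpoint only when it leads to further oral treatment.

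The size cannot be determined, because the protocol does not give the share of patients with chest or back acne. All that can be said without an assumption is the effect of each misread participant: 2.0 points with 50 participants or 3.3 points with 30.

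Two stronger readings go too far. One is a percentage bias built from assumed truncal prevalence and persistence. Those inputs are not in the document, and the bias would be measured against an all-sites success rule that the protocol never adopts. The other is that the error always favours the drug. For participants with a facial grade below 3 at entry, the result depends on how an undefined case is handled, and a truncal responder could be left uncounted.

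The point deserves correction before enrolment, because it decides who may enter and what may be concluded, and neither can be repaired afterwards.

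**What to change.** - **Sections 5.0 and 8.0:** require CASS grade 3 on the face at entry. The baseline statement in section 10.0 then agrees with the inclusion criteria.
- **Sections 1 and 10.0:** name the endpoint as facial CASS grade and limit the efficacy conclusion to facial acne.
- **Baseline examination:** record whether the chest or back is also affected, so that the enrolled group can be described.

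**Cost.** This means wording in four sections and one extra baseline data field, with no added visits, staff or procedures. A few patients with mainly truncal acne become ineligible, and the claim is narrower. Monthly chest and back photography is not needed for this correction. It would add procedures and change the endpoint.

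### The single Photo Reviewer can link each participant's photos and see their order, because every photo carries the participant number and date; a random code and shuffled reading would mask visit order cheaply

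*Protocol*

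**What the plan says.** Protocol section 10.0 (Study Design / Methods, after the CASS table) sets out the reading procedure.

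- **Transfer.** The Data Retriever "will submit any uploaded photos (baseline and at the end of each" month) to the Photo Reviewer by encrypted email, "labeling only with participant number and date of photo". The reviewer is to see photos singly and never opens the chart.
- **Masking.** The reviewer is told neither the drug nor anything about the study, "including that all participants are on the study drug, in order to limit observer bias (blinded").
- **Outcome.** A drop from grade 3 to 2, 1 or 0 is improvement. Staying at 3 or rising is failure, "or requiring additional oral treatment (for example, worsening acne requiring conventional dose isotretinoin"). Success is reported at four months, "in addition to treatment success after each month of treatment".
- **Baseline.** "Baseline photos will all be a grade 3 (moderate) based on study inclusion criteria". Section 8.0 makes the enrolment criterion a clinician's "score of 3, moderate acne, on CASS clinical scale".
- **Numbers.** Section 6.0: "Target enrollment is 50 participants to allow for attrition. Minimum expected enrollment is 30 participants".

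Nowhere does the protocol recode the photos, shuffle them or defer their reading.

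**The concern.** There is no control arm, so efficacy rests on the contrast between the enrolment grade and later grades from one reader, a medical student. In the CASS table, grades 2 and 3 differ mainly in whether less or more than half of the affected area is involved. That is a visual estimate from a photograph, and some photos will be doubtful.

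A reader who knows which photo is later may settle the doubtful ones by expectation. A reader who remembers giving the same participant number a 3 last month may instead repeat it. In either case the success percentage, which is the primary result, would partly reflect the reader's knowledge of the sequence. Section 16.0 says a benefit here could lead to larger randomised studies, so the percentage informs a decision.

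**Working it through.** The protocol gives no figure to reproduce on this point. The check compares what is masked with what the label reveals, and then works out scale.

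**1. What is masked and what is visible**

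| Item | Hidden from the reader? | Source |
|---|---|---|
| Drug, study details, all participants treated | Yes | Section 10.0 |
| Medical chart | Yes | Section 10.0 |
| Which photos belong to the same person | No: participant number on the label | Section 10.0 |
| Order of a person's photos | No: date on the label | Section 10.0 |

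Reading photos singly does not change the last two rows, because number and date travel with each photo. Removing the date alone would not be enough either: photos are sent, and grades recorded, month by month, so the time of arrival also gives the order.

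**2. Effect of one reading**

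Inputs: N = 50 (target) and N = 30 (minimum), section 6.0. Each participant contributes 100/N percentage points to month-four success.

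- 100/50 = 2.0 points
- 100/30 = 3.3 points

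This holds for a participant without additional oral treatment. With such treatment the participant is a failure whatever the photo shows.

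**3. Readings that can affect the stated percentages**

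The baseline grade is taken as 3 by inclusion, so a baseline reading cannot change them. That leaves months 1 to 4.

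- All monthly percentages: 4 × 30 = 120 readings, or 4 × 50 = 200
- Month-four result: 1 × 30 = 30 readings, or 1 × 50 = 50

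These are maxima, assuming every participant supplies every photo and none has additional oral treatment.

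**4. Workload under shuffled reading, baseline included**

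- 5 × 30 = 150 readings, or 5 × 50 = 250
- With at most one photo per participant per session: 250/50 = 5 sessions of up to 50 photos, or 150/30 = 5 sessions of up to 30

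These are the photos already sent under the current procedure.

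**The case against.** The best defence is that the stated masking already weakens the mechanism. The reader does not know the drug or that everyone is treated, and grades each photo on an absolute scale rather than for change. A date shows sequence, but not when treatment began or that improvement is expected. Women also start at least a month after the baseline visit (section 8.0), so dates do not map directly to time on drug. The study is a single-arm proof of concept that reports observations without statistical analysis (section 12.0).

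Much of this stands, and it keeps the point at minor to moderate weight. It does not remove it. Someone trained on a severity scale who receives dated monthly photos of numbered people can reasonably infer follow-up, and no stated safeguard hides the order.

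A reader might infer that the success percentage is inflated. The document does not support that: anchoring on an earlier grade 3 would lower it, and nothing shows which effect would dominate. A reader might also infer that the protocol contradicts its own blinding. It does not, because the blinding it describes never extends to visit order.

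**Conclusion.** The point holds as a cheap improvement to the method, of minor to moderate severity. The labelling rule lets the only reader of the primary endpoint link and order each participant's photos, which leaves the aim of limiting observer bias partly unmet.

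The labelling fact is certain; its effect is not. Neither size nor direction of bias can be derived, and the 2.0 and 3.3 points show only what one changed month-four grade would do. At most 120 readings (30 participants) or 200 (50) can affect the stated percentages, of which 30 or 50 decide the month-four result.

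It would be tempting to add the photos requested after the study period. Section 10.0 asks for them only from participants who continue weekly isotretinoin and does not say that they are graded, so they are not counted.

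**What to change.** Amend the photo procedure in section 10.0 as follows.

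1. **Code.** Replace the participant number and date with a random code for each photo, and remove both from the file name and embedded data. The Data Retriever holds the key.
2. **Export monthly.** Export and code photos at each month's end. Section 14.0 ends access to the medical record at withdrawal but keeps data already collected, so photos taken before a withdrawal are retained.
3. **Grade later, shuffled.** Read after follow-up to month four is complete, in random order mixing participants and visits, baseline included. Allow at most one photo per participant in each session, for example five sessions of up to 50 photos for 50 participants. Putting several photos of one face in the same session would make direct comparison easier. Include all photos of participants who left early.
4. **Merge.** The reviewer returns only code and grade. The Data Retriever merges these, adds failures due to additional oral treatment, and computes the monthly and month-four percentages.

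**Cost.** Protocol wording and a coding list, with the same staff and the same photos. Grades arrive later, and photo scores would be absent from the spreadsheet that the monitoring committee reviews monthly (sections 12.0 and 13.0). Section 13.0 describes that review in terms of laboratory results and surveys, and section 17.0 already withholds response results until analysis, so the loss looks small. Faces may still be recognised, so masking is improved but not complete.
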